Hypothesis b (development of a clinical alert to identify when PVA is occurring with high frequency). To improve the recognition of PVA and support trials focused on PVA prevention, it is necessary to have real-time tools which balance the benefits of identification of potentially injurious forms of PVA against false alarms. The focus of this sub-aim is to develop a decision support system to continuously read in flow and airway pressure waveforms, apply the machine learning algorithms, provide relevant summary data about PVA frequency and subtypes, and potentially alert clinicians when patients have high rates of dangerous forms of PVA. We will build the relevant pipelines necessary for these systems, using raw waveform data from the three different hospitals. We will develop alert algorithms to identify patients who are having frequent PVA, while minimizing false alarms. This will mimic the real-world deployment scenario of detecting PVA on a new patient (not previously seen). The system and alert algorithms will be developed and internally validated from the data available in the existing datasets, evaluating sliding windows of 30-60 breaths to identify patients that exceed thresholds for PVA subtypes during that window (i.e. > 20% of breaths are flow undershoot in that window). This is important because it may not be possible (or desired) to eliminate all forms of PVA, particularly if the PVA event is rare. The unintended consequence of adjusting ventilator settings to eliminate one form of PVA, may result in other forms of PVA, or other consequences such as over-assistance of the patient. We will adjust the alert thresholds to optimize detection of true PVA events, against false alarm rates, with the goal of maintaining false alarm detection as low as possible (i.e. less than 5%). As seen in the preliminary data with DC breaths, on the individual breath level, our false alarm rate is 1/3-1/14 when sensitivity is in the 50-75% range. We anticipate the requirement for a certain number (or percentage) of breaths to be classified as a certain PVA subtype will greatly improve the sensitivity and specificity for identifying patients with frequent PVA.

Additional References for PVA

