Analysis of PVA subtypes leading to DC breaths, and identification of risk factors: Each dataset contains detailed diagnostic data, demographics, ventilator settings, and medication data. Using data from existing datasets, all patients and all days of ventilation will be analyzed to describe the frequency of PVA subtypes leading to DC breaths. For each DC breath (anticipated 3% of all breaths), one of three underlying PVA subtypes will be annotated (Reverse Trigger, Flow Undershoot/Premature Termination, Auto-trigger, Figure 4). Flow undershoot and premature termination represent the same physiologic concepts of inadequate ventilator support, so they will be combined for analysis of DC breaths. We anticipate that RT and Flow Undershoot/Premature Termination will continue to comprise $> 95\%$ of the causes of DC and will be the primary focus of analysis. We will evaluate ventilator and patient specific risk factors for PVA subtypes which lead to DC.

Sample Size and Power: From existing datasets, we are anticipating having over 1,000,000 breaths for analysis, from 371 patients, with more than 1,000 patient days. Based on our preliminary data, 3% of breaths are DC, and 70% of patients have at least one episode of DC. This should give us a minimum of 30,000 DC breaths from 260 patients. This will permit inclusion of dozens of variables in the risk factor analyses, although we anticipate between 3-5 in each model. Analysis will be conducted on the breath and on the patient level.

The goal of the breath level model is to understand why DC occurs when a specific PVA subtype is present. We will create two prediction models, one to identify risk factors for DC related to RT and one to identify DC related to flow undershoot/premature termination. Variables considered in the breath-by-breath model include parameters with biological plausibility to be in the causal pathway for the PVA subtype or DC including ventilator mode (including NAVA), respiratory rate, ventilator rate (RRvent), spontaneous or neural respiratory rate (RRneural) and neural

Asynchrony subtypes leading to Double Cycled Breaths

[figure not shown]

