Figure 4. Asynchrony subtypes leading to DC breaths. Flow undershoot/ premature termination represent inadequate ventilator support for the patient's respiratory drive, while Reverse trigger leading to DC occurs when patient effort begins after lung insufflation. Auto trigger is relatively rare and occurs when a second breath is delivered with no patient effort.

initiation and termination, peak inspiratory pressure (PIP), Tidal Volume, PEEP, inspiratory time, and an estimate for patient effort (Δ Pes, peak Edi, or sEMG). We will first perform univariate analysis on the predictor variables of interest, stratified by DC versus non-DC in each of the subtypes. Mixed logistic regression models will then be created to first control for patient level effects with repeated measurements per patient, retaining variables with an independent association with DC breaths.

The goal of the patient level model is to identify patients who are at high risk for DC. Because RT and flow undershoot/ premature termination are the PVA subtypes which lead to DC over 95% of the time, variables for consideration will focus on risk factors for each of these PVA subtypes, in addition to risk factors for DC specifically. Univariable analysis will examine the Spearman's correlation between the frequency of DC breaths per patient in each PVA subtype category and static patient related variables of interest such as **age**, **gender**, height, body weight, risk factors and severity of lung injury, blood gas data, sedation and analgesia (cumulative dose of drugs, pain and sedation scale). In addition, median values for respiratory parameters from breath-by-breath analysis over the entire 30-minute recording will also be used. Subsequently, patients will be categorized into groups based on the frequency of DC breaths from each subtype. Those with DC occurring in more than 5% of breaths will be labeled DC patients for analysis. Our preliminary data supports this occurs in approximately 20% of patients. Subsequently, mixed logistic regression models will be created to identify the patient specific factors associated with DC, stratified by each of the PVA subtypes.

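### The breath-level double-cycling models name only a patient effect, so standard errors for ventilator settings that change mainly between recordings may be understated.

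*Combined protocol and SAP*

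**What the plan says.** Section H plans two breath-level models, one for double cycling (DC) arising from reverse trigger and one for DC arising from flow undershoot or premature termination. Their purpose is stated under *Sample Size and Power* for Asynchrony Specific Aim 1: "The goal of the breath level model is to understand why DC occurs when a specific PVA subtype is present". The candidate predictors mix settings (mode, ventilator rate, PEEP, inspiratory time) with quantities that can differ from breath to breath (tidal volume, neural timing, a measure of effort). After univariate screening the plan continues: "Mixed logistic regression models will then be created to first control for patient level effects with repeated measurements per patient", and variables independently associated with DC are kept. No day, recording, site or measurement-method level, residual correlation structure or robust variance is named.

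The data are described as "over 1,000,000 breaths for analysis, from 371 patients, with more than 1,000 patient days", with every ventilation day included and a recording lasting 30 minutes. The event count is put at 30,000 ("This should give us a minimum of 30,000 DC breaths from 260 patients"), and the capacity claim follows from it: "This will permit inclusion of dozens of variables in the risk factor analyses, although we anticipate between 3-5 in each model". Under Specific Aim 2, Hypothesis A, the plan accepts that asynchrony rates may differ between days in the same patient.

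**The concern.** The data have three levels: breath, recording (or day) and patient. The text names the outer one. A patient random intercept absorbs stable differences between children. It does not absorb differences between Monday's and Wednesday's recording in the same child, which could come from sedation, respiratory drive or stage of illness.

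For a predictor that is nearly constant within a recording, the information lies between recordings and between patients. A model with only a patient intercept counts each breath as a fresh observation given the patient, so unmodelled recording-to-recording variation stays out of the standard error. The retention step then works with p-values that are too small and could keep a setting that has no effect. Settings are the risk factors a reader would be most inclined to act on, and Section H itself links the cause of DC to the choice of therapeutic strategy.

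**Working it through.** **1. The plan's own figures reproduce.**
- Patients: 235 + 74 + 62 = 371 (expected REDvent patients plus the sEMG and Edi cohorts).
- DC breaths: 1,000,000 × 0.03 = 30,000.
- Patients with any DC: 371 × 0.70 = 259.7, about 260.

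**2. A middle level exists.** 1,000 patient-days / 371 patients = 2.7 days per child. 1,000,000 / 1,000 = 1,000 breaths per patient-day, or 33 per minute over 30 minutes. That fits about one recording per day, although the plan does not say so.

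**3. Breaths in each model.** Subtype shares come from the REDvent preliminary data in Section H.
- Flow undershoot/premature termination: (13.8% + 5.1%) × 1,000,000 = 189,000 breaths, about 189 per recording. DC risk: 0.03 × 0.452 / 0.189 = 0.072.
- Reverse trigger: 1.9% × 1,000,000 = 19,000 breaths. If the 0.03 × 0.525 × 1,000,000 = 15,750 DC breaths attributed to reverse trigger are counted on top, the total is 34,750, about 35 per recording, with DC risk 15,750 / 34,750 = 0.45.

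**4. Rough guide.** For a covariate constant within a recording, the design effect is 1 + (m − 1) × ICC, where the ICC is the residual within-recording correlation (assumed 0.01 to 0.10).
- m = 35: 1 + 34 × 0.01 = 1.3, to 1 + 34 × 0.10 = 4.4.
- m = 189: 1 + 188 × 0.01 = 2.9, to 1 + 188 × 0.10 = 19.8.

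**5. Simulation of the false-positive rate.** Taken from the documents: 371 patients, a mean of 2.7 recordings each, and the breath counts and DC risks in step 3 (risks rounded to 0.07 and 0.45). Assumed: a no-effect covariate fixed within a recording, with half its variance between and half within patients; patient SD 1.0 logit; recording SD 0 to 1.0 logit; two-sided 0.05. There were 200 runs per cell.

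| Recording SD (logit) | 0 | 0.25 | 0.5 | 1.0 |
|---|---|---|---|---|
| Flow undershoot/premature termination, patient intercept only | 0.07 | 0.20 | 0.42 | 0.74 |
| Reverse trigger, patient intercept only | 0.06 | 0.09 | 0.23 | 0.44 |
| Either model, ordinary logistic with patient-clustered robust SE | 0.06–0.07 | 0.07 | 0.06 | 0.04–0.06 |

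Simulation error is about ±0.03 near 0.05 and up to ±0.07 for the larger rates.

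**6. A second simulation with different settings agrees.** It covered the flow undershoot/premature termination model with 260 patients, 3 recordings each, 170 at-risk breaths per recording and patient SD 0.8. Recording SDs of 0.3, 0.5 and 0.8 gave false-positive rates of 26%, 43% and 61%. The true spread of the estimate was 1.8, 2.5 and 3.4 times the reported standard error.

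**The case against.** A reader might infer that the plan tests settings as if a million breaths were independent. The documents do not support that. A mixed model with a patient effect assumes independence only given the patient, and the difference is large: with no recording-level variation, the planned model stays at 0.06 to 0.07, while an analysis that ignores clustering gives 0.56 to 0.80. Nor does any breath-level model use a million breaths, because each is confined to one asynchrony subtype.

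Other parts of the opposing case also stand:
- The plan does not rule out a day-level effect; it is silent. The final SAP allows GEE or mixed models for repeated measures, and gives an autoregressive structure and sandwich errors for ventilator settings and respiratory measures. Neither provision is tied to Section H, so a patient-only model remains the natural reading.
- Nothing in the documents says that settings are fixed within a recording. This is reasonable for mode, set rate and PEEP over 30 minutes. Tidal volume, neural timing and effort can vary by breath and are less affected. Effort and neural rate, if included, might also explain some of the variation between recordings; the simulations do not allow for this.
- The recording-level variance is not given anywhere, so an unconditional statement that the errors are far too small would go beyond the evidence.
- The subtype shares come from the REDvent cohort and may not hold in the pooled data.
- The sample-size paragraph does give patients and patient-days beside the breath count, and expects only 3 to 5 variables per model.

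What survives is narrower. The one clustering level named is not enough if propensity varies between recordings, and Aim 2 itself allows that it may.

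**Conclusion.** The point holds in conditional form. Followed as written, the breath-level models understate the uncertainty for predictors that change mainly between recordings, provided that double-cycling propensity varies between recordings of the same child. The consequence ranges from negligible (no such variation) to a false-positive rate of roughly 0.2 to 0.4 at a recording SD of 0.5 logit. Inflation is about half as large in the reverse-trigger model as in the other model at SDs of 0.25 and 0.5. These sizes rest on assumed variances and on the inference that some settings are nearly constant over 30 minutes; the direction does not depend on the particular values.

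This is worth correcting because the remedy is simple and the affected predictors are the ones most likely to be acted on. It concerns an associational secondary analysis and leaves the trial's primary outcome untouched.

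**What to change.** In Section H, Aim 1, specify for the breath-level models either a random effect for recording (or day) nested within patient, or patient-clustered robust standard errors. The robust option, checked above with an ordinary logistic fit, brought the false-positive rate back to 0.04 to 0.07 in both models. It estimates a population-averaged odds ratio, so the plan should say which estimate is intended. The nested effect addresses the same gap but was not simulated. If the sandwich methods in the final SAP are meant to apply here, say so.

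In *Sample Size and Power*, base the number of variables a model can carry on patients and recordings, not on the 30,000 DC breaths.

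The cost is one extra variance component or an estimation option, and wider intervals for setting-level risk factors. No new data are needed.

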Because the pre-specified plan was to use a negative binomial model, those findings have been presented in the main results, but because the model does not appropriately fit the data due to the highly influential outliers, the conclusions and abstract results reflect the more appropriate proportional odds model. This model was agreed upon by the study statistical team and DSMB statisticians in June 2024 at the final DSMB meeting.

PiMax was planned to be modeled with linear regression, with truncation of values >100. In the analysis, no transformation could satisfy the assumptions of linear regression, with poor model diagnostics and non-normality of residuals. PiMax was therefore modeled with the proportional odds model given the non-parametric nature of the data. No specific categories were created for PiMax, but instead it was treated as a rank-based variable with comparisons of ranks between groups, adjusting for blocking variables and confounders (oxygenation index). The model allowed us to compare the odds of a higher PiMax ranking for the REDvent vs. usual care groups. Table 1 has been revised and now presents the description of all outcome variables, initial planned analyses, and modifications to initial proposed analyses and the timing of those changes. In addition, since all outcomes are presented as adjusted analyses, Table 2 details the four main modeling approaches used in these analyses, and interpretation of the model intervention parameter estimates.

References

1. [name] RG, Smith LS, Zimmerman JJ, et al. Pediatric Acute Respiratory Distress Syndrome: Definition, Incidence, and Epidemiology: Proceedings From the Pediatric Acute Lung Injury Consensus Conference. *Pediatric Critical Care Medicine*. Jun 01 2015;16(5_suppl):S23-S40. doi:10.1097/PCC.0000000000000432
2. [name] RG, Hotz JC, Klein MJ, et al. A Phase II randomized controlled trial for lung and diaphragm protective ventilation (Real-time Effort Driven VENTilator management). *Contemp Clin Trials*. Jan 2020;88:105893. doi:10.1016/j.cct.2019.105893
4. Firth D. Bias Reduction of Maximum Likelihood Estimates. *Biometrika* 1993. p. 27-38.

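### Section H, asynchrony Aim 1: the only adjusted patient-level model cuts double-cycled breath frequency at 5%, which keeps about half of its information at the stated 20% share

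*Combined protocol and SAP*

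**What the plan says.** Section H, under the methods for asynchrony Aim 1, describes a patient-level model meant to find children at high risk of double-cycled (DC) breaths. The univariable step correlates DC frequency per patient, by subtype, with patient characteristics (Spearman), so the frequency is uncut there. Patients are then grouped: "Those with DC occurring in more than 5% of breaths will be labeled DC patients for analysis". On the choice of 5%, the text adds only this: "Our preliminary data supports this occurs in approximately 20% of patients". The adjusted step follows: "mixed logistic regression models will be created to identify the patient specific factors associated with DC, stratified by each of the PVA subtypes". No adjusted patient-level model of the uncut frequency is planned for this aim.

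The Aim 1 sample size paragraph expects data "from 371 patients, with more than 1,000 patient days". It continues: "Based on our preliminary data, 3% of breaths are DC, and 70% of patients have at least one episode of DC". From this it concludes: "This should give us a minimum of 30,000 DC breaths from 260 patients". It gives no effect size, alpha or power for the patient-level model.

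Elsewhere the same documents avoid cutting. Asynchrony Aim 2 keeps asynchrony rates per patient continuous and looks for dose response. On PiMax, the final SAP (July 2024) says: "No specific categories were created for PiMax, but instead it was treated as a rank-based variable with comparisons of ranks between groups".

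**The concern.** DC frequency is a percentage with some spread: about 30% of children have none and about 20% exceed 5%. After the cut, a child just above 5% counts the same as one far above it, and a child just below 5% counts the same as one with no DC breaths. The share of patients above a threshold describes the cut; it is not a reason for choosing it.

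The cut falls on the step that decides which patient factors are independently associated with DC. Modest true risk factors are then easier to miss. The unadjusted and adjusted steps can also disagree merely because the outcome changed scale between them. Finally, the wording leaves open whether 5% refers to all DC breaths or to those of one subtype, and this changes how many children carry the label.

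**Working it through.** **Inputs from Section H.** 371 patients; over 1,000,000 breaths; 3% of breaths DC; 70% of patients with any DC breath, so about 30% at zero; about 20% of patients above 5%. Pooled over breaths in the REDvent preliminary cohort, 52.5% of DC breaths were reverse trigger and 45.2% flow undershoot or premature termination.

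**Assumptions.** Two-sided alpha 0.05 and correlations of 0.10 to 0.30 between one normal risk factor and latent DC frequency. The plan gives neither for this model.

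**The plan's own figures.** 0.03 × 1,000,000 = 30,000 DC breaths and 0.70 × 371 = 259.7, about 260 patients. Both reproduce. They count children with any DC breath; the number above the cut is 0.20 × 371, about 74.

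**Information kept by the cut.** In a proportional odds model, information is proportional to 1 − Σp³, where p are the shares in each tied group.

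- Cut, 20/80: 1 − 0.2³ − 0.8³ = 0.480.
- Uncut, 30% tied at zero: 1 − 0.3³ = 0.973.
- Ratio: 0.480 / 0.973 = 0.49.

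The normal-theory formula φ(z)² / [p(1−p)] at p = 0.20 also gives 0.49. So 371 children carry the information of about 0.49 × 371 = 182. This step needs no effect size.

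**Power, all DC breaths together.** A normal approximation for r = 0.15 runs as follows. atanh(0.15) × √368 = 2.90, so uncut power is Φ(2.90 − 1.96) = 0.83. With the cut, 2.90 × √0.49 = 2.03 and power is Φ(0.07) = 0.53. That overstates the gap somewhat, because it ignores the ties at zero in the uncut analysis. A simulated rank test at n = 371, with 30% of children tied at zero, gives:

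| Assumed r | Uncut (rank) | Cut at 20% | Loss, points |
|---|---|---|---|
| 0.10 | 0.443 | 0.273 | 17 |
| 0.15 | 0.756 | 0.513 | 24 |
| 0.20 | 0.952 | 0.776 | 18 |
| 0.25 | 0.995 | 0.929 | 7 |
| 0.30 | 1.000 | 0.985 | 2 |

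A second simulation gave about 16 to 22 points for r = 0.10 to 0.20 and 1 to 2 points at 0.30. Together the range is roughly 16 to 24 points for modest associations and almost nothing for strong ones.

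**Power within a subtype.** This depends on how each child's DC breaths divide between subtypes, which is not reported. Two extremes bracket it. Both use n = 371, 30% of children with no DC, about 20% above 5% overall, a mean near 3% and 750 breaths per child.

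- Every child's DC breaths split half and half: about 5% of children exceed 5% within a subtype. At r = 0.15 power falls from 0.75 to 0.25. Across runs at r = 0.15 to 0.20 the loss was about 40 to 50 points.
- Every child has a single subtype, assigned independently of the risk factor: about 63% are at zero and about 11% exceed 5% within a subtype. Uncut against cut power is 0.25 against 0.27 (r = 0.15), 0.43 against 0.45 (r = 0.20) and 0.75 against 0.77 (r = 0.30). There is no loss.

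**The case against.** A high-frequency label suits the stated goal of finding high-risk children. The Aim 3 alert section also explains why frequent asynchrony may matter more than rare events. The uncut frequency is used in the Spearman step, breath-level mixed models are planned alongside, and Aim 2 keeps rates continuous. This is a secondary analysis added by amendment, and no trial outcome depends on it. All of this stands, and it keeps the point small. It does not supply an adjusted patient-level analysis of the uncut frequency, and the chance of exceeding 5% can be read from a model of the full frequency.

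The size of the loss can also be disputed. A reader might infer a fixed penalty of 17 to 50 points of power. The documents do not support that: they give no effect size here. The only one in Section H, a partial r of 0.3, belongs to the Aim 2 mediation analysis, and at that strength the overall loss at n = 371 is 1 to 2 points.

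A reader might also infer that stratifying by subtype must make matters worse. That is not established either. The 52.5% and 45.2% shares are pooled over breaths, not within children, and Section H associates the two subtypes with different mechanisms, so many children may have mainly one. The single-subtype extreme shows no penalty.

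The inputs are also soft. The 70% matches the 46 of 65 REDvent preliminary patients; the other two cohorts had DC rates of 4% and 1%. The 750 breaths per child is an assumption; Section H implies about 835 (54,284 / 65) or 2,700 (1,000,000 / 371). The simulations use one predictor and one observation per child, not the planned mixed multivariable model.

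**Conclusion.** The point holds as a minor one. The plan dichotomises DC frequency before its only adjusted patient-level model for this aim, without a reason for the threshold. At the plan's own 20% share and 30% at zero, the cut keeps about 49% of the information. That figure rests only on those two shares and on a proportional odds (or normal) effect across the scale.

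The power cost is conditional: roughly 16 to 24 points for assumed correlations of 0.10 to 0.20 at n = 371, and 1 to 2 points at 0.30. By subtype it lies between about none and about 40 to 50 points, and the documents do not allow it to be narrowed. The unclear reference of the 5% threshold is a separate gap that should be closed in any case.

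**What to change.** In the Aim 1 patient-level paragraph of Section H, make the main adjusted model one for the full DC frequency, fitted for each subtype. Two options fit the data: DC breaths out of total breaths in a beta-binomial or quasi-binomial model, or the rank-based proportional odds model that the final SAP already uses for PiMax. Keep the 5% label as a secondary or descriptive summary. State whether 5% refers to all DC breaths or to those of each subtype, and give a reason for the value if it stays.

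The cost is a wording change and a different model call, with no new data. The downside is interpretive: the odds ratio then describes a higher DC frequency, not crossing 5%.
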